9. STATISTICAL CONSIDERATIONS	
A. Sample Size.....	
B. Analyses.....	
10. HUMAN SUBJECTS PROTECTIONS.....	
A. Adequacy of Protection Against Risks.....	

	B. Potential Risks to Subjects and Protections.....
	C. Potential Benefits of the Proposed Research
	D. Risk-to-Benefit Ratio.....
	E. Inclusion of Women and Minorities.....
	F. Subject Confidentiality.....
	G. Study Modification/Discontinuation.....
11.	PUBLICATION OF RESEARCH FINDINGS
12.	REFERENCES

SUMMARY

Patient support after stroke requires a long-term commitment, supporting the patient as they move through “nodes” of acute care, post-acute in-hospital care, subacute care (inpatient rehab, extended stay, etc.), and chronic care. The current standard of stroke care is the Joint Commission (JC)-certified Comprehensive Stroke Center or Primary Stroke Center (CSC/PSC) care system, a collection of proven processes of care, but an approach with a focus on acute care (and to a lesser extent the post-acute in-hospital care), with little coordination of care of the patient after discharge. The overall goal of C3FIT is to assess if patient outcomes are improved when the CSC/PSC system is supplemented with an Integrated Stroke Practice Unit (ISPU) system of care, a patient-centric model of care involving the patient’s caregiver that coordinates care from the acute management through the rehabilitation and recovery of the patient.

The specific aim of this project is to assess superiority of patient-centric outcomes between the CSC/PSC and ISPU models in a cluster-randomized pragmatic trial conducted at approximately 18 clinical sites in the United States (US). The primary aim focuses on differences in 12-months post stroke quality of life (QOL) using the Stroke Impact Scale (SIS) and patient function using the Simplified Modified Rankin Scale (smRS). Secondary aims include other patient/caregiver-centered outcomes, including: (1) short-term function and QOL using the SIS and smRS; (2) control of stroke risk factors; (3) mortality, recurrent stroke rates, and hospital readmission rates; (4) Time At Home; (5) patient depression, using the Patient Health Questionnaire (PHQ-9); and (6) caregiver strain, using the Caregiver Strain Index (CSI). Finally, we aim to determine whether there are patient subgroups specifically responsive or resilient to the intervention, according to effect modification by age, race, sex, and socio-economic status (income and education).

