- (1) The ISPU approach will improve secondary stroke outcomes relative to the CSC/PSC approach, including: SIS and smRS at 3 and 6 months, risk factor control, stroke recurrence rates, hospital readmission rates, mortality in the first 12 months, time at home, patient depression, and caregiver strain.
- (2) The ISPU benefit in SIS and smRS will persist after the protocol-based post-acute coordination of in-home/facility care is terminated (at 12 months).
- (3) Patient characteristics (specifically age, race, sex, income, and education) will affect the primary or secondary intervention differences.

B. Primary and Secondary Outcomes

Primary and secondary outcomes are documented in Table 1 and described below.

- *Primary outcomes* include patient function and QOL using the SIS and smRS at 12-months post-stroke.
- *Secondary outcomes* are patient/caregiver-centered and include: (1) short-term patient function and QOL using the SIS and smRS (at 3 and 6 months); (2) the proportion of patient with risk factors controlled at target (at 3, 6, and 12 months); (3) mortality in the first 12 months, time to first recurrent stroke, and number of hospital readmissions per participant month over the first 12 months; (4) Time At Home (proportion of survival time spent at home); (5) patient depression, using the Patient Health Questionnaire (PHQ-9; at 3, 6, and 12 months); and (6) caregiver strain, using the Caregiver Strain Index (CSI; at 3, 6, and 12 months).

Table 1. Study Outcome Measures and Assessment Frequency					
C3FIT OUTCOMES	VARIABLES	ASSESSMENT FREQUENCY (By Month)			
		H	3	6	12
Functional Assessment	Stroke Impact Scale	X	X ⁺	X ⁺	X ⁺
Quality of Life	Simplified Modified Rankin Scale	X	X ⁺	X ⁺	X ⁺
Stroke Risk Factors					
(1) Blood pressure control at target*	Standard Systolic and Diastolic Measurement	X	X	X	X
(2) Lipid control at target*	Standard Lipid Panel or, at a minimum, LDL (Blood Draw, repeated only if patient's cholesterol is elevated at baseline, if LDLC%≥70mg/dl, or if patient is on a statin)	X	X	X	X
(3) Diabetes control at target*	Standard HBA1c (Blood Draw, repeated only if patient's blood glucose is elevated at baseline or if HBA1C%≥7mg/dl)	X	X	X	X
(4) Smoking status*	Question(s) to assess patient smoking status	X	X	X	X
(5) Body Mass Index (BMI)*	Weight and hip circumference	X	X	X	X
(6) Diet	Question(s) to assess patient adherence to recommendations of the American Heart Association (AHA).	X	X ⁺	X ⁺	X ⁺

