6. BASELINE AND FOLLOW-UP ASSESSMENTS AND LABORATORY EVALUATIONS

The following outlines the Data Paradigms for Stroke Mobile based on obtained values for various scales and data points utilized. The guidelines establishing blood pressure and cholesterol goals are from the American Heart and Stroke Association.⁸

A. On-Study/On-Intervention Evaluations

The schedule of evaluations occurring after randomization while the subject is on-study and on (or about to start) intervention along with allowable time window in which evaluations may take place (± 30 days with a target of ± 14 days) is shown in Tables 7 and 8. Primary and secondary outcomes are considered a mandatory part of the protocol; remaining measures will be collected if patient/caregiver are able and/or available.

Table 7. Data Collection Paradigm: ISPU Arm, Stroke Central and Stroke Mobile

Item/Metric	In Hospital Prior to Discharge	Post Discharge Visit											
		Day 0-14	Month of Visit to Home/Facility										
		1	2	3	4	5	6	7	8	9	10	11	12
Informed Consent Confirmed	X	X	X	X	X	X	X	X	X	X	X	X	X
Demographics (Age, Gender, Race/Ethnicity, Marital Status, Zip Code of Residence, Income, and Education)*	X			X			X						X
Caregiver/Family identified*	X			X			X						X
Medical Record Number (MR #)*	X												
Get-With-The-Guidelines (GWTG) in-hospital data*	X												
Patient Medical History	X			X			X						X
Complications* ¹	X			X			X						X
National Institutes of Health Stroke Scale (NIHSS)*	X	X	X	X	X	X	X	X	X	X	X	X	X
Stroke Subtype*	X												
Prior stroke/Transient Ischemic Attack (TIA)*	X												
Risk factor profile* ²	X												X
Cholesterol panel or LDL*	X			X			X						X
Hemoglobin A1C (HBA1C)*	X			X			X						X
Perceived Support				SRU			SRU						SRU
Stroke Impact Scale (SIS)				SRU			SRU						SRU
Simplified Modified Rankin Scale (smRS)	X			SRU			SRU						SRU
Blood Pressure (BP) Control: at target	X	X	X	X	X	X	X	X	X	X	X	X	X
Lipid Control: LDL, at target	X			X			X						X
Diabetes Control: HBA1C, at target	X			X			X						X
Smoking Status	X	X	X	X	X	X	X	X	X	X	X	X	X
Body Mass Index (BMI)	X	X	X	X	X	X	X	X	X	X	X	X	X
Diet Assessment	X	X	X	X	X	X	X	X	X	X	X	X	X
Exercise Assessment	X	X	X	X	X	X	X	X	X	X	X	X	X
Mortality surveillance		X	X	X	X	X	X	X	X	X	X	X	X
Recurrence surveillance		X	X	X	X	X	X	X	X	X	X	X	X
Readmission surveillance		X	X	X	X	X	X	X	X	X	X	X	X
Time at Home		X		SRU			SRU						SRU
Depression History	X												
Depression: Patient Health Questionnaire (PHQ-9)		X	X	X	X	X	X	X	X	X	X	X	X

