## **2. Definitions and classification of covariates**

The covariates used in the incremental models include measures of stroke severity, demographic factors, and traditional cerebrovascular risk factors.

- Measures of stroke severity
  - Discharge location, classified as discharged home vs. not home (skilled nursing, rehabilitation center, etc.).

- Discharge mRS, categorized as 0, 1, 2, 3 or 4 or more (noting relatively few patients with discharge mRS of 5).
- Discharge NIH Stroke Scale (NIHSS), categorized into approximate quartiles of 0, 1, 2-4 or 5+
- Stroke subtype (hemorrhage vs. infarction)
- Demographic factors
  - Age, considered as a continuous factor
  - Male sex
  - Race/Ethnicity, categorized as non-Hispanic white (NHW) versus not NHW (including both other races and Hispanic participants)
  - A summary neighborhood index of socio-economic status (nSES) based on previously published methods, including six variables representing wealth/income, education and occupation: (1) log of median household income, (2) log of median value of owner-occupied housing units, (3) proportion of households receiving interest, dividend, or net rental income, (4) proportion of adults aged  $\geq 25$  years with a high school diploma, (5) proportion of adults aged  $\geq 25$  years with college degree, and (6) proportion of people employed in executive, managerial or professional occupations.
- Baseline cerebrovascular risk factors
  - Cigarette smoking, categorized as current vs. non-current (past or never)
  - Hypertension as a dichotomous variable
  - Dyslipidemia as a dichotomous variable
  - Diabetes as a dichotomous variable
  - Atrial fibrillation or irregular heartbeat as a dichotomous variable
  - Sedentary activity (defined as a score of 0-No Physical Activity or 1-Sedentary or sitting most of the time)

Because the mixed models will include baseline assessment of the outcome variable (i.e., outcomes include measures at times 0, 3, 6, and 12 months), covariates directly related to the outcome being assessed will be excluded from the model. That is, variables will not be used as both an outcome and as a predictor in the same model. For example, discharge mRS will not be included in the models predicting treatment differences in mRS, and baseline hypertension will not be included in models assessing treatment differences in SBP. Rather, changes from baseline to the 3, 6 and 12-month visits will be assessed using contrast statements.

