### **3.2. Modified Rankin Score (mRS)**

The mRS is a 7-point scale, ranging from 0 (normal) to 6 (dead), where at baseline the scores were from 0 to 5 (discharged dead were excluded from the study). During follow-up, patients were scored a 6 at the 3, 6 and 12-month follow-up if the patient died before the respective follow-up (even if the patient missed intervening visits). The mRS will be dichotomized as “good outcomes” of 0 to 2 points, and “poor outcomes” of 3 to 6 points. Analysis will use a mixed model approach (implemented through GLIMMIX) with the treatment-specific proportion of “good outcomes” modeled at months 0, 3, 6, and 12 (reported with the p-value for treatment differences at each time point). The primary outcome will be treatment differences in the change in the proportion with good outcomes between months 0 and 12, but differences to months 3 and 6 will also be estimated. These differences will be estimated with the same 4-level incremental adjustments, and with both unadjusted and inverse-probability weighted adjustment. Effect modification will be assessed by age, sex, race/ethnicity, stroke sub-type, stroke severity (discharge NIHSS dichotomized at 0 to 1 versus 2+), and nSES. With the discharge mRS as an outcome, the analysis will not be adjusted for baseline mRS.

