### **3.3. Stroke Impact Scale (SIS)**

The SIS is a continuous outcome variable with a range from 0 to 100 which will be analyzed identically to continuous intervening factors measured at 4 timepoints (including the analysis with inverse probability weighting). We do note that: 1) after approximately half the patients were recruited, a decision was made to not collect SIS at baseline; however, it is quite reasonable to assume that this decision will give rise to data missing at random and the missingness will be addressed by the mixed models, and 2) the baseline SIS collected were the “long form” of the questionnaire (96 items); however, the 16 items in the short form used at 3, 6 and 12 months are a subset of the long form, and these items will be extracted and scored identically with the follow-up assessments. The analysis of SIS will employ analysis for a continuous factor, but will follow the modeling approach described above for mRS, specifically reporting treatment differences in mean SIS rather than treatment differences in the proportion with good mRS outcome (primary outcome as treatment difference in the change in mean SIS between baseline and 12 months, 4-level incremental models, with/without inverse probability weighting, assessment of effect modifiers, etc.).

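### The SAP tests socio-economic effect modification only through a neighbourhood index, so two of the five modifiers in secondary hypothesis 3, the patient's own income and education, are not tested at patient level

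*SAP*

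**What the plan says.** Protocol section 1.A gives secondary hypothesis 3 as "Patient characteristics (specifically age, race, sex, income, and education) will affect the primary or secondary intervention differences". The protocol Summary states the matching aim as identifying responsive or resilient subgroups "according to effect modification by age, race, sex, and socio-economic status (income and education". Both statements appear in the ISPU and the CSC/PSC versions of the protocol.

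Table 7 in section 6 of each version has the row "Demographics (Age, Gender, Race/Ethnicity, Marital Status, Zip Code of Residence, Income, and Education", scheduled before discharge and again at follow-up. The row carries an asterisk: these items are collected only where the patient or caregiver can supply them.

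The SAP list of modifiers, in 3.1 for the intermediate factors and in 3.2 for the mRS, reads "Effect modification will be assessed by age, sex, race/ethnicity, stroke sub-type, stroke severity (discharge NIHSS dichotomized at 0 to 1 versus 2+), and nSES". SAP 3.3 applies the mRS approach to the SIS, including "4-level incremental models, with/without inverse probability weighting, assessment of effect modifiers, etc". SAP section 2 defines the last item on the list as "A summary neighborhood index of socio-economic status (nSES) based on previously published methods, including six variables representing wealth/income, education and occupation". Its components are medians and proportions for an area, for example "log of median household income".

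The SAP does not use patient-level income or education anywhere. It gives no reason for using the index instead and does not say that hypothesis 3 was changed. Protocol section 9.B mentions subgroups in general terms and names no modifier.

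**The concern.** Hypothesis 3 asks whether a person's own income or education changes the effect of integrated care. The planned test asks whether the effect differs between richer and poorer neighbourhoods. These are different questions. A patient with little schooling and low income who lives in an affluent area is scored as high on nSES. Because the index merges income, housing value, investment income, schooling and occupation, even a clear nSES interaction could not be attributed to income or to education, which the protocol names separately.

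What is at stake is one part of one secondary hypothesis. If the SAP is followed, the report will have no prespecified result for income or education, and a null nSES interaction would say little about either. Any patient-level analysis added afterwards would be post hoc, although the hypothesis was prespecified.

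**Working it through.** The point rests on comparing texts. The documents give no power or sample size for any interaction, so there is no figure of the plan's to reproduce.

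**Step 1. Match the modifiers in hypothesis 3 to the SAP.**

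| Named in Protocol 1.A | Modifier in SAP 3.1 to 3.3 | Level |
|---|---|---|
| Age | Age | Patient |
| Sex | Sex | Patient |
| Race | Race/ethnicity | Patient |
| Income | Only within nSES | Area |
| Education | Only within nSES | Area |

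Three of the five are tested directly and two are not tested at patient level. The SAP also adds stroke subtype and discharge NIHSS, which hypothesis 3 does not name.

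**Step 2. Check whether the patient-level data are planned.** They are. Table 7 schedules both items before discharge in both arms, subject to the availability condition.

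**Step 3. Illustrate what a proxy does to the test.** This step uses assumptions that are not in the documents:
- Modification acts only through the patient's own socio-economic status.
- nSES has correlation r with that status. The documents give no value, so r is shown over 0.3 to 0.7.
- The reference is a fully observed patient-level test with 80% power at two-sided 0.05.

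With both variables standardised and a patient-level interaction slope g, the slope seen through nSES is r × g. The sample needed for equal power rises by 1/r². The reference test has non-centrality 1.960 + 0.842 = 2.802, so power through nSES is Φ(2.802r − 1.960).

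| r | 1/r² | 2.802r − 1.960 | Power through nSES |
|---|---|---|---|
| 0.3 | 11.1 | −1.119 | 13% |
| 0.5 | 4.0 | −0.559 | 29% |
| 0.7 | 2.0 | 0.001 | 50% |

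These rows show the direction and rough scale of the loss. They do not estimate this trial's power.

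**Step 4. Count the added tests.** SAP 3.1 to 3.3 cover six intermediate factors, the mRS and the SIS, which makes eight outcomes. Two interactions each gives 8 × 2 = 16. This is a minimum: income or education in more than two categories, four adjustment levels and weighted re-analysis would all add to it.

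**The case against.** The strongest reply is that nSES is a legitimate way to measure the construct. The Summary speaks of socio-economic status, and the index contains area income and area education. For care delivered in the home, neighbourhood may matter in its own right. There is also a plausible practical reason for the choice. Income and education are collected only where available, whereas Protocol 4.F has zip code of residence identified for all stroke admissions to determine inclusion, so an area index may be far more complete. All of this supports keeping nSES. It does not support replacing the named variables without comment, since hypothesis 3 calls them patient characteristics and the SAP gives no such reason.

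Three stronger readings are tempting, and the documents do not support them.

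- *Socio-economic status, or hypothesis 3 as a whole, has been dropped.* It has not. Three of the five modifiers are tested directly, and the other two have an area-level proxy.
- *The trial cannot answer the question.* The data are scheduled for collection and would allow a later analysis. What is missing is a prespecified one.
- *Because sites are randomised and recruit locally, the nSES interaction is largely a comparison of a few sites.* No document gives the variance of nSES, its intraclass correlation or its geographic unit. Protocol 4.C extends recruitment to contiguous counties in order to widen diversity and rural coverage, which suggests spread within sites. Nothing shows that individual income is free of site clustering either.

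**Conclusion.** The mismatch stands. As written, the SAP leaves two of the five modifiers in hypothesis 3, income and education, untested at patient level, although both are scheduled for collection before discharge in both arms. That count comes directly from the documents.

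A reader might take the multipliers of 11, 4 and 2 as the sample-size penalty in this trial. They are illustrative only: they depend on an assumed correlation and on modification acting solely through the patient's own status. If neighbourhood matters directly, they do not apply.

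The consequence is limited to a secondary subgroup hypothesis for which no power is claimed. The primary treatment estimates do not change. The correction is still worth making before analysis, because it uses data already planned and lets the trial address its own stated hypothesis.

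**What to change.** In SAP 3.2 and 3.3, add treatment-by-income and treatment-by-education interactions for mRS and SIS at 12 months. In SAP 3.1, add the same two as exploratory analyses. Specify:

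- **Values.** Use those recorded before discharge. A later recorded value may fill a blank for education only. Income at 3, 6 or 12 months follows the stroke and the start of the intervention, so recovery or treatment could have changed it. It should not stand in for a baseline modifier.
- **Categories.** State the income and education categories in advance.
- **Missing data.** State a rule for patients with no pre-discharge income, and for those with no education recorded at any visit.
- **nSES.** Keep it as a covariate and an additional modifier, and report its interaction as a neighbourhood result.

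Alternatively, amend hypothesis 3 and the Summary aim to neighbourhood socio-economic status and give the reason. While editing, the authors should also say whether modification will be assessed for the secondary outcomes. Hypothesis 3 covers them, but SAP section 4 names no modifiers and at most inherits them where 4.3 to 4.5 refer back to earlier approaches.

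The cost is SAP or protocol wording, with no new data collection. The downsides are incomplete income and education, and two more exploratory interactions per outcome (at least 16 over all eight). Numbers will be thin in SAP 3.1, where each factor is analysed only among patients not in control at discharge.

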### **3.3. Stroke Impact Scale (SIS)**

The SIS is a continuous outcome variable with a range from 0 to 100 which will be analyzed identically to continuous intervening factors measured at 4 timepoints (including the analysis with inverse probability weighting). We do note that: 1) after approximately half the patients were recruited, a decision was made to not collect SIS at baseline; however, it is quite reasonable to assume that this decision will give rise to data missing at random and the missingness will be addressed by the mixed models, and 2) the baseline SIS collected were the “long form” of the questionnaire (96 items); however, the 16 items in the short form used at 3, 6 and 12 months are a subset of the long form, and these items will be extracted and scored identically with the follow-up assessments. The analysis of SIS will employ analysis for a continuous factor, but will follow the modeling approach described above for mRS, specifically reporting treatment differences in mean SIS rather than treatment differences in the proportion with good mRS outcome (primary outcome as treatment difference in the change in mean SIS between baseline and 12 months, 4-level incremental models, with/without inverse probability weighting, assessment of effect modifiers, etc.).

## **4. Secondary Outcomes**

### **4.1. Time-to-event secondary outcomes (mortality, recurrent stroke, and rehospitalization)**

The number of days between discharge and death, recurrent stroke or rehospitalization will be calculated, and treatment differences in the times will be assessed using hierarchical proportional hazards models (i.e., using a RANDOM statement for site if conversion, or fixed effect with no conversion). The same incremental modeling approach (crude, adjusted for stroke severity, further adjusted for demographics, and finally adjusted for risk factors) will be employed. It is possible that the number of events may be relatively small (particularly for death and recurrent

stroke), introducing concerns for the use of too many covariates relative to the number of predictors. Should this be the case, a “restricted” number of covariates will be considered, specifically using NIHSS as the single index of severity, using age and race/ethnicity as the indexes of demographics, and hypertension as the single index of risk factors. These will be added in this order up to the point where there are at least 10 events for each factor introduced (i.e., perhaps, not even all these predictors can be considered).

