Analysis of the primary analysis will focus on intervention differences in mean SIS and smRS scores at 12 months. In addition, the mixed models will be used to assess the SIS and smRS outcomes at 12 months, allowing the hierarchical nature of the data to be reflected (patients within Sites), and providing an accounting for data that are not missing completely at random. Analyses of the secondary outcomes of time either rehospitalization or subsequent stroke will be assessed using proportional hazards analysis. In order to incorporate the hierarchical nature of these data, this analysis will be implemented using packages such as the SURVIVAL procedure from the SUDAAN package (Research Triangle Institute, Research Triangle Park, NC).

Analysis of the QOL secondary outcome will follow the analysis approach as the primary analysis and will have similar power (i.e., ability to detect intervention differences of magnitude of a half-standard-deviation). The study will also focus on identifying specific subgroups who are particularly responsive or resilient to intervention differences.

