#### **4.2. Time-at-home**

The proportion of the “time at risk” (defined as the patient being alive and with known status) to be at home will be calculated for each patient, where patients with a no time at risk will be excluded from analysis. Time at home is defined by subtracting time during hospitalization, rehabilitation, skilled nursing from the follow-up time (defined as the time from discharge to last follow-up, death or withdrawal date). Treatment differences in the time-at-home will be assessed in a hierarchical regression model (patients within sites). A 4-level incremental modeling approach like that used for other outcomes will be employed, with the modification that the time at risk will be considered in all models. The first step in considering the time at risk is to assess an interaction with treatment, and should this interaction be significant ( $p < 0.10$ ) the analysis will be stratified and the median value for time at risk. After this determination, the analysis will proceed in a similar manner as other outcomes with the exception that time at risk will be included as a covariate in all models.

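### The readmission rate that the protocol names as a secondary outcome is never estimated: protocol 9.B and SAP 4.1 plan only a time-to-rehospitalization analysis

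*SAP*

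**What the plan says.** Three places bear on this outcome.

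- **Protocol, Primary and Secondary Outcomes (1.B), both arm versions.** One item of the secondary outcome list sets two kinds of measure side by side: "time to first recurrent stroke, and number of hospital readmissions per participant month over the first 12 months". Recurrent stroke is a time to first event. Readmission is a count divided by person-time. Secondary hypothesis 1, just above it, is also worded in terms of rates: "risk factor control, stroke recurrence rates, hospital readmission rates, mortality in the first 12 months".
- **Protocol, Analyses (9.B), both arm versions.** "Analyses of the secondary outcomes of time either rehospitalization or subsequent stroke will be assessed using proportional hazards analysis". No count or rate analysis of readmissions follows.
- **SAP 4.1.** Rehospitalization is grouped with mortality and recurrent stroke as a time-to-event outcome: "The number of days between discharge and death, recurrent stroke or rehospitalization will be calculated, and treatment differences in the times will be assessed". The model is a proportional hazards regression in which site is the only clustering term.

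SAP 4.2 is the one other place where hospital stays enter an analysis: "Time at home is defined by subtracting time during hospitalization, rehabilitation, skilled nursing from the follow-up time".

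**The concern.** A rate of readmissions and a time to rehospitalization answer different questions. The first uses every readmission in the year. The second, with one event time per patient, stops looking at a patient after the first readmission.

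The distinction matters here because the ISPU intervention continues through monthly visits for a year. A first-event analysis does not register readmissions prevented after the first one. It can also show a benefit when the first readmission is only delayed and the total is unchanged. In either case the hypothesis about readmission rates is left without an estimate.

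Readmission is not peripheral to the trial. The pilot results in protocol Table 3 list a reduction in readmissions as an effect of the model, and the benefits section names fewer readmissions as a possible gain.

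**Working it through.** **Text comparison.** The documents give no power, event rate or dispersion for readmission (the power section covers only the SIS), so there is no stated figure to reproduce.

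| Place | Quantity | Method |
|---|---|---|
| Protocol 1.B | Readmissions per participant-month, 12 months | None given there |
| Protocol 9.B | Time to rehospitalization | Proportional hazards |
| SAP 4.1 | Days from discharge to rehospitalization | Proportional hazards with site effect |
| SAP 4.2 | Proportion of time at home | Regression, patients within sites |

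No row, and no other SAP section, estimates the quantity in the first row. SAP 4.1 names no recurrent-event method and no patient-level term for repeated events, so one event per patient is the natural reading.

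**Illustration of size.** Let μ be the mean number of readmissions per patient over a full 12 months, and P0 the probability of none. Each patient ever readmitted contributes one first event, so

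share unused = 1 − (1 − P0)/μ,

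with P0 = exp(−μ) under a Poisson model, or P0 = 1/(1 + μ) under a negative binomial with dispersion k = 1.

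*From the 12.7% in protocol Table 3.* The table gives this background figure for stroke readmission without a time frame. Taking it, as an assumption, as the share of patients ever readmitted in the year gives 1 − P0 = 0.127.

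- Poisson: μ = −ln(0.873) = 0.1358; share = 1 − 0.127/0.1358 = 0.065.
- k = 1: μ = 1/0.873 − 1 = 0.1455; share = 1 − 0.127/0.1455 = 0.127.

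*From assumed means.*

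| μ | Poisson | k = 1 |
|---|---|---|
| 0.3 | 1 − 0.2592/0.3 = 0.136 | 1 − 0.2308/0.3 = 0.231 |
| 0.5 | 1 − 0.3935/0.5 = 0.213 | 1 − 0.3333/0.5 = 0.333 |
| 0.8 | 1 − 0.5507/0.8 = 0.312 | 1 − 0.4444/0.8 = 0.444 |

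With 1,262 patients all followed for 12 months, μ = 0.3 means about 379 readmissions (1,262 × 0.3), of which about 51 (Poisson) to 87 (k = 1) would be repeats.

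**Ascertainment.** Table 7 of the ISPU version schedules readmission surveillance at every monthly visit. Table 7 of the CSC/PSC version schedules it at months 3, 6 and 12. Table 1 in both versions lists rehospitalization at months 3, 6 and 12. A count built from every ISPU visit would therefore rest on more frequent questioning in one arm.

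**The case against.** The strongest reply is that SAP 4.1 does what protocol 9.B told it to do. This stands. A reader might infer that the SAP dropped a protocol analysis, but the documents do not support that: the time-to-event plan is already in the protocol, and the disagreement is between 1.B and 9.B. It does not supply the missing rate, however; it only moves the origin of the problem.

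A reader might also take it as stated that repeat readmissions are discarded. SAP 4.1 does not say that only the first event counts. That is an inference from one event time per patient and the absence of any recurrent-event method. It is the likeliest reading, and if repeats were meant to enter, the SAP would have to say how.

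It is also fair to say that repeat hospital stays are not wholly invisible, because they reduce time at home over all of follow-up. But that measure counts days and pools hospital with rehabilitation and skilled nursing, so it cannot yield a readmission rate.

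The loss may be modest. Patients need a pre-morbid score of 0-1 and must be expected to survive a year. Nothing in the documents suggests that any benefit would be confined to second and later readmissions.

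Finally, a count analysis has a weakness of its own. Longer recall intervals in the CSC/PSC arm could undercount repeat admissions there and bias the rate ratio against ISPU. Time to first rehospitalization is not immune, but may be less exposed. This objection stands and shapes the fix.

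**Conclusion.** The point holds as an unreconciled outcome definition. If the plan is followed exactly, the secondary outcome defined in 1.B is left without an estimate. That conclusion rests on the text alone and does not depend on any assumed rate.

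The size of the loss is not known. The illustrative shares, about 6-13% using the 12.7% figure and 14-44% at assumed means of 0.3 to 0.8, rest on full 12-month follow-up, on dispersion between Poisson and k = 1, and on readmission levels that the documents do not give for this trial. The 12.7% may be neither a 12-month nor an all-cause figure. It would go too far to say that a third or more of the readmission information is lost: that needs a mean near 0.5 or above with over-dispersion, for which the documents offer no source.

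The issue concerns one secondary outcome for which no power is claimed. It does not touch the SIS or Rankin analyses.

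**What to change.** Reconcile protocol 1.B, protocol 9.B and SAP 4.1 before readmissions are compared by arm.

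1. Add the analysis that 1.B defines: a negative binomial mixed model for the number of readmissions per patient, with log months at risk (alive and with known status, as in SAP 4.2) as offset, a random site effect and the same four incremental covariate models. Report the rate ratio with its confidence interval. A recurrent-event model would serve equally well.
2. Report the proportional hazards analysis alongside it, and state explicitly that it concerns the first rehospitalization.
3. Count readmissions from the 3-, 6- and 12-month assessments that both arms share, or from medical records in both arms. Report the difference in surveillance frequency as a limitation, since monthly contact may still improve recall in the ISPU arm.

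If the sponsor prefers time to first rehospitalization as the outcome, 1.B should be redefined openly and the reason given. That removes the contradiction but leaves the rate hypothesis unanswered.

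The analysis cost is one further model. The data cost is less certain. SAP 4.2 needs time spent in hospital, which does not establish that separate admission episodes are recorded, so this should be checked first. The result will also depend on comparable capture of repeat admissions in the two arms.
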